Study rationale	HFpEF, characterized by elevated left filling pressures and exercise intolerance, is an increasingly common clinical syndrome. Exercise intolerance is the primary symptom and significantly impacts quality of life. An elevated pulmonary capillary wedge pressure (PCWP), a marker of increased left atrial pressure (LAP), is associated with reduced exercise capacity, likely due to pressure transmission to the lungs, and increased mortality. Research has shown that increasing the heart rate at rest can reduce LAP in patients with HFpEF, potentially enhanced by a shortened AV delay. However, patients mainly experience symptoms during low-intensity exercise, where the effects of accelerated pacing remain unknown.
Primary objective	To assess the impact of accelerated pacing with AV-regulation on the PCWP during exercise in patients with HFpEF, particularly at lower intensities of exertion, to offer insights into pacing-based interventions to ultimately enhance exercise tolerance and quality of life.
Secondary objective(s)	To assess the impact of accelerated pacing with AV-regulation on cardiac output, stroke volume, peripheral oxygen extraction and shear wave velocity.
Endpoints	The primary endpoint is the change in pulmonary capillary wedge pressure for each pacing frequency compared to the intrinsic heart rate, assessed at rest and during exercise (cycle ergometry at 10 and 25 Watts of resistance). Secondary endpoints include changes in cardiac output, stroke volume, and peripheral oxygen extraction from the intrinsic heart rate to the pacing frequency associated with the greatest reduction in PCWP, both at rest and during exercise (cycle ergometry at 10 and 25 Watts). Additionally, changes in shear wave velocity at each pacing frequency relative to the intrinsic heart rate will be assessed.
Sample Size	20

Date of anticipated First Participant First Visit (FFPV)	01/10/2025
Date of anticipated Last Participant Last Visit (LPLV)	30/09/2026
Expected study duration for a single participant	3 weeks

STUDY FLOWCHART

Schedule of events – Study specific procedures & assessments

UZ Leuven

Procedures/ Assessment	Screening	Study visit
Visits / Contacts	Visit 1	Visit 2
Timing (weeks)		Week 3
Visit Window (days)	1 day	1 day
Informed consent	X ¹	
Inclusion / Exclusion criteria	X	
Demographics	X	
Medical / Surgical history	X	
Physical examination	X	
Weight / Height	X	X
Vital Signs	X	X
12-lead ECG	X	X
Haematology sampling	X	
Coagulation sampling	X	

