2.1 Study objectives

In this study, we plan to address the impact of accelerated pacing with AV-regulation on the PCWP at rest and during exercise in patients with HFpEF. We hypothesize that accelerated pacing with AV-delay regulation reduces PCWP at rest and during exercise up to an optimal pacing rate beyond which no further benefit is observed.

In this study, we aim to:

- Evaluate the effect of accelerated pacing with AV-optimization on PCWP at rest.
- Investigate the impact of accelerated pacing with dynamic AV delay programming, while avoiding truncation, on PCWP during exercise at two distinct (low) intensities (10 and 25 Watts) using a semi-supine cycle ergometer.
- Assess the change in CO, SV and peripheral oxygen extraction at the pacing frequency corresponding to the lowest PCWP compared to the intrinsic heart rate. This approach allows examination not only of the effects of pacing on backward cardiac function (as reflected by PCWP), but also on forward cardiac function. By doing so, it excludes the possibility that a reduction in PCWP is merely due to a decreased CO.
- Evaluate the effects of different pacing frequencies on SWV as a non-invasive marker of myocardial stiffness

Ultimately, we aim to offer insights into novel pacing-based interventions to enhance exercise tolerance and quality of life in patients with HFpEF.

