2.3 Secondary endpoints

The secondary endpoints are:

- The change in CO at the pacing frequency corresponding to the greatest reduction in PCWP compared to the intrinsic heart rate
- The change in SV at the pacing frequency corresponding to the greatest reduction in PCWP compared to the intrinsic heart rate
- The change in peripheral oxygen extraction at the pacing frequency corresponding to the greatest reduction in PCWP compared to the intrinsic heart rate
- The change in SWV for each pacing frequency. The SWV at the intrinsic heart rate is defined as the average of the SWV at the intrinsic heart rate heart rate before and after each pacing step.

Cardiac output is measured via the direct Fick principle, dividing VO_2 by the peripheral oxygen extraction (SaO_2 - SvO_2). SV is calculated as CO divided by HR.

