6.2 Statistical analysis

This is a prospective, single-arm, multicentre, interventional study in which each patient serves as their own control:

- A two-sided significance level of 0.05 will be used for all statistical tests.
- Data will be analyzed using Python, SPSS and Stata statistical software.
- Descriptive statistics of baseline variables will be used to summarize baseline characteristics.
 - Categorical variables will be presented as number and percentage.
 - Continuous variables will be presented as mean \pm standard deviation or median with interquartile range, depending on the Shapiro-Wilk test for normality.
- Comparison of hemodynamic parameters (PCWP, CO, SV, peripheral oxygen extraction) and SVV will be performed using paired student t-test or Wilcoxon-Mann Whitney test whichever will be appropriate.
- Pearson's or Spearman's correlation coefficients, whichever will be appropriate, will be computed to assess the relationship between changes in PCWP and changes in SVV

Endpoint	Statistical analysis methods
Primary	paired student t-test or Wilcoxon-Mann Whitney test
Secondary	paired student t-test or Wilcoxon-Mann Whitney test
Exploratory	descriptive statistics, Pearson's or Spearman's correlation coefficient

7 Data handling

A study-specific Data Management Plan (DMP) will be developed by the Sponsor providing a.o. further details on data flows, data handling, processing and discrepancy management.

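### Up to 18 secondary contrasts are each tested at an unadjusted two-sided 0.05, so isolated significant SWV or flow results should not count as findings

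*Combined protocol and SAP*

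**What the plan says.** Section 6.2 sets one error rule: "A two-sided significance level of 0.05 will be used for all statistical tests". The same section says: "Comparison of hemodynamic parameters (PCWP, CO, SV, peripheral oxygen extraction) and SVV will be performed using paired student t-test", with a Wilcoxon test as the alternative (SVV there is read as SWV). The table closing 6.2 gives primary and secondary endpoints identical tests. The exploratory row contains only "descriptive statistics, Pearson's or Spearman's correlation coefficient".

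The synopsis defines the flow endpoints: "Secondary endpoints include changes in cardiac output, stroke volume, and peripheral oxygen extraction from the intrinsic heart rate" to the rate with the greatest PCWP reduction, "both at rest and during exercise (cycle ergometry at 10 and 25 Watts". Section 2.3 adds "The change in SWV for each pacing frequency". Section 2.2 gives three pacing rates at rest and three during exercise, and Appendices 3 and 4 schedule SWV at each pacing step at rest, 10 W and 25 W.

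Neither the protocol nor its appendices give a testing order, an adjustment, a lead secondary, or a statement that secondary p-values are descriptive. The opening of section 6 says a separate SAP will supplement this text. That SAP is not among the documents.

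**The concern.** The plan tests its secondary endpoints in the same way as the primary, and its exploratory row does not include them. Read as written, any secondary p-value below 0.05 is a significant result.

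With nine SWV comparisons, one small p-value at one rate and one workload could be reported as pacing changing myocardial stiffness, a question that section 1 describes as open in HFpEF. A chance CO or extraction result in one of three conditions could be read as pacing improving or impairing forward flow.

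The nine primary PCWP contrasts raise their own multiplicity question, which is separate from this point.

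**Working it through.** **1. The plan's own figure.** Section 6.1 assumes a mean difference of -2 mmHg and an SD of 2.5 mmHg, so d = 2/2.5 = 0.8. An exact paired t-test at two-sided 0.05 has power 82.1% at n = 15 and 84.8% at n = 16. The stated 16 is therefore reproduced to within one patient (15/0.955 = 15.7 gives 16 with a Wilcoxon allowance), and 16/0.8 = 20. This covers a single PCWP contrast. No error rate is stated for the secondary family.

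**2. Counting the contrasts.**
- Flow: CO, SV and extraction (3) × rest, 10 W, 25 W (3) = 9.
- SWV: 3 rates × 3 conditions = 9. This reads the SWV endpoint together with the measurement schedule in Appendices 3 and 4.
- Total: 18. The correlation of PCWP change with SWV change is not counted, because 6.2 places it in the exploratory row.

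Eighteen is a ceiling. Appendix 3 lists no SWV measurement in the pacing-off period between +40 and +60 bpm. The resting +40 contrast therefore lacks its after value, and the resting +60 contrast its before value, relative to the baseline defined in 2.3. On a strict reading, 16 contrasts can be computed as defined.

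**3. Which nulls can hold together.** Section 2.3 gives SV = CO/HR. If CO is unchanged and pacing raises HR by Δ, SV changes by the factor HR/(HR + Δ), which is below 1. For an assumed 70 bpm and Δ = 20, this is 70/90 = 0.78. A significant SV fall would then be real. Removing the three SV tests leaves 18 − 3 = 15 that can be null together: six for CO and extraction, nine for SWV.

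**4. Chance of at least one false positive.** If the tests were independent, the rate is 1 − 0.95^k:
- k = 15: 0.54
- k = 9: 0.37

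The tests are not independent. CO is VO₂ divided by extraction, and SWV contrasts share pacing-off baselines. The documents give no correlations, so a range is assumed. Simulated paired t-tests, n = 16, common correlation, all nulls true:

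| Correlation | 15 tests | 9 SWV tests |
|---|---|---|
| 0.25 | 0.49 | 0.34 |
| 0.5 | 0.38 | 0.28 |
| 0.75 | 0.24 | 0.19 |
| 0.9 | 0.15 | 0.13 |

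The expected number of false positives does not depend on correlation: 15 × 0.05 = 0.75, and 9 × 0.05 = 0.45.

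**5. A more structured check.** CO and extraction were tied at 0.8 to 0.95 within a condition and 0.2 to 0.8 between conditions. SWV tests were correlated at 0.25 to 0.8, and the two blocks were independent. The 15-test rate is then 0.29 to 0.49, and the rate for CO and extraction alone 0.13 to 0.22.

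**6. Precision for CO.** At n = 16 the 95% CI half-width is 2.131/√16 = 0.53 SD of the paired differences. A non-significant CO test is therefore compatible with a true fall of about half an SD or more.

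**The case against.** The strongest case against is that this is a 20-patient, single-arm, acute mechanistic study meant to offer insights. Strict family-wise control of secondary endpoints is not customary there, and an SAP is still to come. That stands as an argument against heavy adjustment. It does not answer a rule that applies 0.05 to every test: an SAP that only supplements 6.2 leaves that rule in force.

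Some nulls may also be false. Section 1 cites higher SWV at higher pacing rates, although in patients without HFpEF, so some SWV results may be real. Fewer patients may reach the highest rates, because pacing steps stop at the age-predicted maximum. Both points make the figures conditional. Neither removes the inflation.

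Three stronger readings are tempting and are not supported:
- *A false positive is more likely than not.* The independence value for 18 tests is 1 − 0.95^18 = 0.60, but it needs SV to be null and all tests independent. For the 15 tests, the rate stays below one half at every assumed correlation from 0.25 upward.
- *Overlap between CO and extraction makes matters worse.* Testing nearly the same quantity twice lowers the family-wise rate.
- *The claim in 2.1 is undermined by false positives.* That section says of the CO comparison: "By doing so, it excludes the possibility that a reduction in PCWP is merely due to a decreased CO". The conclusion would rest on CO not falling. The risk there is a non-significant result read as no fall, and a stricter alpha would increase that risk.

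**Conclusion.** The concern holds in a limited form. Every secondary contrast is tested at full 0.05, outside the exploratory row, with nothing to limit what may be claimed. If the 15 contrasts that can be null together are all null, the chance of at least one nominally significant result is about 0.24 to 0.49 at assumed correlations of 0.25 to 0.75. For the nine SWV tests it is 0.19 to 0.34, and still 0.13 at correlation 0.9. These figures rest on the assumed correlations, on 16 patients contributing to every contrast, and on reading the SWV endpoint as covering all three conditions.

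This is an inexpensive improvement to how results may be described. It does not threaten the primary analysis, and it has lower priority than multiplicity in the primary PCWP contrasts.

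**What to change.** In 6.2, and carried into the SAP before any analysis:

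1. Restrict the two-sided 0.05 rule to the primary endpoint.
2. Report the nine SWV changes as estimates with 95% CIs and no significance claim. If a claim is wanted, apply Holm across the nine; the smallest p-value is then compared with 0.05/9 = 0.0056.
3. Report CO, SV and extraction in all three conditions as estimates with 95% CIs, with any p-values labelled nominal.
4. Judge whether CO is preserved from its 95% CI, not from a non-significant test, and word the statement in 2.1 to match.

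Do not test CO in a fixed order that stops at the first non-significant result. If CO were truly unchanged at 10 W and that test came first, the sequence would continue only 5% of the time, so a real fall at 25 W or at rest could be claimed at most 5% of the time.

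The change needs no extra patients, measurements or visits. Its cost is that an isolated nominal p<0.05 for a secondary endpoint can no longer be claimed as a finding. If Holm is chosen for SWV, power at the first step falls from 84.8% to about 51% (n = 16, d = 0.8 borrowed from the PCWP planning assumption, exact paired t-test at 0.0056).

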2.2 Primary endpoints

The primary endpoints are:

- The change in PCWP at each pacing frequency (+20 bpm, +40 bpm, +60 bpm) with its corresponding optimal AV delay at rest, compared to PCWP at the intrinsic heart rate.
- The change in PCWP at each pacing frequency (+10 bpm, +30 bpm, +50 bpm) using dynamic AV delay programming, while avoiding truncation, compared to PCWP at the intrinsic heart rate during exercise (cycle ergometry at 10 and 25 Watts)

The PCWP at the intrinsic heart rate is defined as the average of the PCWP at the intrinsic heart rate heart rate before and after each pacing step.

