2.4 Study design

This is a **prospective interventional** study, as it actively adjusts pacing rate and AV delay in real time to assess their acute effects on PCWP at rest and during exercise.

The study is a **single arm** study. All patients undergo the pacing protocol (Figure 3 and 4) as an internal pairwise comparison is made between different pacing conditions and the intrinsic heart rate.

The study is **unblinded**. All measurements will be performed bedside, allowing patients to follow the different steps of the protocol. As a result, they will naturally become aware of pacing adjustments, making partial blinding unfeasible. While this may introduce some expectation bias in subjective measures such as palpitations or exertion intolerance, the primary (PCWP) and secondary endpoints (CO, SV, peripheral oxygen extraction, SWV) are objective physiological measures. Therefore, the absence of blinding does not compromise the validity of the results.

The study is **multicenter**, as both UZ Leuven and Jessa Hospital will recruit patients and implement the study protocol.

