5.4.3 Pharmacovigilance / Materiovigilance

Any incidents related to the use of a medical device should be reported to the Competent Authorities according to the materiovigilance guidelines.

6 Statistics and data analysis

A study-specific Statistical Analysis Plan (SAP) will be developed by the Sponsor, to supplement the information below with further details.

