6.1 Sample size determination

The sample size calculation is based on the expected difference in PCWP between pacing conditions. A power analysis determined that 16 participants are required to achieve a power of 80% and a significance level of 5% (two-sided), assuming a mean difference of -2 mmHg and a standard deviation of 2.5 mmHg. To account for potential dropout, the study will enroll 20 participants.

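### Section 6.2 names an independent-samples test (Wilcoxon-Mann-Whitney) as the alternative to the paired t-test in a design where every comparison is within patient

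*Combined protocol and SAP*

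**What the plan says.** Section 6.2 describes the trial as an "interventional study in which each patient serves as their own control". Section 2.4 says that "an internal pairwise comparison is made between different pacing conditions and the intrinsic heart rate". The primary endpoint in section 2.2 is a change within the patient: at rest, PCWP at each paced rate "with its corresponding optimal AV delay at rest, compared to PCWP at the intrinsic heart rate", with a matching definition for exercise at 10 and 25 W. The reference value is the average of that patient's own pacing-off readings before and after the step.

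For the test, section 6.2 says the comparisons "will be performed using paired student t-test or Wilcoxon-Mann Whitney test whichever will be appropriate". The endpoint table repeats the same two tests in its primary and secondary rows. The signed-rank test does not appear. No criterion for choosing between the two tests is given. The one normality criterion in the section, "depending on the Shapiro-Wilk test for normality", decides only how baseline variables are summarised.

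Section 6.1 bases 16 participants on 80% power and a two-sided 5% level, "assuming a mean difference of -2 mmHg and a standard deviation of 2.5 mmHg". It does not say whether 2.5 mmHg is the SD of the paired difference or of PCWP in one condition. Section 6 opens by promising a separate SAP "to supplement the information below with further details".

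**The concern.** The Mann-Whitney test compares two independent samples. Applied here, it would rank all paced and all intrinsic readings together and ignore which two came from the same patient. Differences between patients in their general level of PCWP then count as noise. The design is built to remove exactly that noise: Appendix 3 compares each paced value with the same patient's readings on either side of it in order to limit spontaneous variability and carry-over.

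There are nine primary PCWP comparisons (three rates in each of three states: rest, 10 W, 25 W), plus the secondary ones. Any of them sent to the non-parametric route would lose power, by an amount that grows with the within-patient correlation. Because the choice of test is open, different pacing rates could be judged by tests of very different sensitivity, in a study whose purpose is to compare rates. The choice could also be made after the data are seen.

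**Working it through.** **Inputs.** From section 6.1: difference -2 mmHg, SD 2.5 mmHg, two-sided 5%, n = 16, 20 enrolled. Not in the documents, so varied: the within-patient correlation ρ, or equivalently the SD of PCWP across patients within one condition, s. The main reading takes 2.5 mmHg as the SD of the paired difference. Since the variance of a difference is 2s²(1-ρ), s = 2.5/√(2(1-ρ)). This gives s = 1.77 at ρ = 0, 2.5 at 0.5, 3.95 at 0.8 and 5.59 at 0.9.

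**Reproducing the 16.**
- Paired, normal approximation: ((1.96 + 0.84) × 2.5/2)² = 12.3, so 13.
- Paired t-test, noncentral t with noncentrality 0.8√n: power is 79.0% at n = 14, 82.1% at n = 15 and 84.8% at n = 16, so 15 are needed.
- Dividing 15 by 0.955, the large-sample efficiency of signed-rank relative to the t-test under normality, gives 15.7, so 16.
- Unpaired: 2 × 12.3 = 24.5, so 25 per group.

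The stated figure therefore fits a paired analysis and not an unpaired one.

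**Why pairing matters.** At n = 16 the paired test has an expected standardised difference of 0.8 × √16 = 3.2. An unpaired comparison at ρ = 0.8 has 2/(3.95 × √(2/16)) = 1.43, below the critical value of 1.96.

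**Power on the same simulated data** (normal, 20,000 replicates per cell, two-sided 5%):

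| ρ | s (mmHg) | Mann-Whitney, n = 16 | Mann-Whitney, n = 20 |
|---|---|---|---|
| 0 | 1.77 | 84.8% | 92.3% |
| 0.3 | 2.11 | 73.7% | 84.6% |
| 0.5 | 2.50 | 58.2% | 72.8% |
| 0.7 | 3.23 | 31.7% | 44.5% |
| 0.8 | 3.95 | 14.5% | 22.2% |
| 0.9 | 5.59 | 2.3% | 3.1% |
| 0.95 | 7.91 | 0.1% | 0.2% |

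In every row signed-rank is about 82% (n = 16) and 91% (n = 20), and the paired t-test about 85% and 92-93%.

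**Non-normal data, n = 16.** This is where the alternative test would be expected to be used.
- Heavy-tailed errors (t, 3 df): Mann-Whitney 69.7%, 15.6% and 1.9% at ρ = 0.5, 0.8 and 0.9; signed-rank about 91%.
- Skewed errors: Mann-Whitney 65.3%, 16.8% and 2.2%; signed-rank 82-83%.

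**Type I error, n = 16.** Mann-Whitney 4.6% at ρ = 0, 0.8% at 0.5, and below 0.1% at 0.8 and 0.9. The test is conservative.

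**Other reading: 2.5 mmHg is the SD within each condition, n = 16.** Mann-Whitney against signed-rank is 56% v 52% at ρ = 0, 58% v 82% at 0.5, 64% v 99% at 0.8, and 68% v about 100% at 0.9.

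No power figure can be given for cardiac output, stroke volume, oxygen extraction or shear wave velocity, because the documents state no effect size or SD for them.

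**The case against.** The strongest reply is that this is a slip of the pen. The surrounding text is plainly paired, and the sample size reproduces only on a paired basis; 16 is even what a signed-rank calculation would give. That is plausible. But the same wording stands three times, and the SAP still to come is described as adding to this text, not replacing it. Section 8.3 also rules out planned deviations from the protocol, so running signed-rank would conflict with the protocol as it stands.

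The second reply is that the low power figures apply only to comparisons actually sent to Mann-Whitney, and most might go to the t-test. This is right, and it limits the size of the harm. Suppose, as an assumption the protocol does not make, that a Shapiro-Wilk test at 5% on the paired differences triggers the switch, with 2.5 mmHg as the SD of the difference and n = 16:
- Normal data: about 5% of comparisons switch. Power for the whole procedure is 85%, 81% and 80% at s = 2.5, 4 and 6, against 85-86% if the alternative were signed-rank. The loss is about 1 to 5 points.
- Heavy-tailed differences (t, 3 df): 28-29% switch. Power is 84%, 72% and 68%, against 92-93%. The loss is about 9 to 25 points.

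A different rule would give different figures, and the protocol has none.

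Third, a near-total loss needs a correlation of about 0.9 and the paired-difference reading of 2.5 mmHg. Under the other reading Mann-Whitney stays at 56-68% for correlations from 0 to 0.9. This also stands. Finally, a significant result from Mann-Whitney would still be credible when the correlation is positive; the risk is a missed effect.

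**Conclusion.** The concern holds. The named non-parametric test is wrong for the design, in the primary and secondary analyses alike. For a PCWP comparison sent to it at n = 16, with 2.5 mmHg as the SD of the paired difference, power falls from about 82% with signed-rank to 58% at correlation 0.5, 15% at 0.8 and 2% at 0.9. There is no loss at correlation 0, but that requires PCWP to vary between patients with an SD of only 1.77 mmHg. If 2.5 mmHg is the SD within a condition, the loss is still large at correlations of 0.5 or more, but not near-total. The effect across the whole analysis cannot be fixed, because neither the correlation nor the selection rule is given. The wording should be corrected before any data are analysed.

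**What to change.** In the section 6.2 text and in the primary and secondary rows of its table, replace the Wilcoxon-Mann-Whitney test with the Wilcoxon signed-rank test on the within-patient change. Add one sentence that fixes the choice of test before the data are seen, based on the paired differences. Carry the same wording into the SAP.

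The better choice rule is the paired t-test for every comparison, with signed-rank as a sensitivity analysis. All pacing rates are then judged by one test. The price is small: with the heavy-tailed errors above, the paired t-test has about 88% power at n = 16, against about 91% for signed-rank. The alternative is a named normality test on the paired differences at a stated level. It can be pre-specified, but it flagged heavy-tailed differences in only 28-29% of runs at n = 16, and it still allows different tests at different rates.

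The cost is three replacements and one added sentence. With 2.5 mmHg as the SD of the paired difference, signed-rank keeps about 82% power at 16 patients, some 3 points below the paired t-test, so 16 (20 enrolled) need not change. Section 6.1 should also say which SD the 2.5 mmHg is. No clinical procedure is affected.

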The myPACE trial demonstrated that personalized accelerated pacing at rest, with a median lower rate of 75 bpm compared to the standard setting of 60 bpm, led to improvements in quality of life, NT-proBNP levels, physical activity, and device-detected atrial fibrillation (23). In contrast, the RAPID-HF study investigating pacemaker implantation with rate-responsive pacing in HFpEF patients with CI found no significant improvement in $\text{VO}_{2\text{peak}}$ and VO_2 at VAT (24). This lack of effect may be attributed to several factors, including the small sample size ($n = 29$), the absence of accelerated pacing at rest, and a suboptimal chronotropic response during exercise. Specifically, excessive heart rate increases may compromise CO in HFpEF due to their impaired diastolic filling and a blunted pressure-volume relationship (25-27). Conversely, an insufficient heart rate rise may fail to adequately enhance chronotropic function or reduce PCWP, thereby limiting hemodynamic benefit. To address these uncertainties, we aim to investigate hemodynamic responses across multiple pacing frequencies. Moreover, this study has focused on high-intensity exercise, evaluating outcomes beyond the anaerobic threshold. In contrast, our study targets low-intensity exertion.

Shear wave velocity as a marker of ventricular stiffness in HFpEF

An additional parameter we will evaluate in this study is shear wave velocity (SWV). This imaging technique provides insights into myocardial stiffness by assessing the propagation speed of naturally occurring myocardial shear waves following mitral valve closure. A study by Salerno et al. demonstrated that higher pacing frequencies are associated with increased SWV, indicative of

elevated ventricular stiffness (28). However, these findings were observed in a population without HFpEF. In patients with HFpEF, who are characterized by increased ventricular stiffness and a steep EDPVR, the effects of pacing on ventricular stiffness and SVV is unknown. These insights may aid in the pathophysiological understanding of pacing strategies designed to improve diastolic function and exercise tolerance in patients with HFpEF.

Study rationale and objective

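### The exploratory correlation of PCWP change with SWV change has no stated unit of analysis; if the up-to-nine steps per patient are pooled, a simple Pearson or Spearman test is invalid

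*Combined protocol and SAP*

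**What the plan says.** Section 6.2 plans Pearson or Spearman coefficients, as appropriate, "to assess the relationship between changes in PCWP and changes in SVV". The endpoint table in that section lists the correlation as exploratory, beside descriptive statistics. The same section adds: "A two-sided significance level of 0.05 will be used for all statistical tests". It makes no exception for exploratory tests.

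Both quantities are defined step by step. Section 2.2 takes the PCWP change at +20, +40 and +60 bpm at rest and, for exercise, "The change in PCWP at each pacing frequency (+10 bpm, +30 bpm, +50 bpm) using dynamic AV delay programming", at 10 W and again at 25 W. Section 2.3 defines the SWV change for each pacing frequency. For both measures the reference is the mean of the pacing-off values before and after the step.

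Section 6.2 names no unit of analysis for the correlation, no method for repeated measures, and no adjustment for pacing rate or workload. Section 6 promises a separate SAP with further details, which is not among the documents.

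**The concern.** Pearson and Spearman tests assume independent pairs. Here the pairs may be clustered within patients, and neighbouring steps share a pacing-off reference. Pooling them would overstate the amount of information and make p-values too small.

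There is also a possible common cause. Section 2.1 hypothesises that pacing lowers PCWP up to an optimal rate. The background section on shear wave velocity cites a study in which "higher pacing frequencies are associated with increased SWV". If both measures respond to pacing rate, a coefficient pooled over rates will be non-zero even when, at a given rate, patients with a larger SWV change do not have a different PCWP change.

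This is the only planned analysis that relates stiffness to filling pressure. With the unit left open, the choice between pooled, per-step and per-patient versions could be made after the data are seen, and a mechanism could be reported that comes from clustering or from pacing rate alone.

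**Working it through.** **The plan's own figure.** The documents give no figure for the correlation. The sample size in section 6.1 rests on one paired PCWP comparison, "assuming a mean difference of -2 mmHg and a standard deviation of 2.5 mmHg". Read as the SD of paired differences, at two-sided 0.05 and 80% power, the noncentral t gives n = 15 (power 82.1%; 84.8% at 16). Allowing for Wilcoxon efficiency, 15/0.955 = 15.7, so 16. Then 16/(1 - 0.20) = 20. The stated 16 and 20 are reproduced.

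**Pairs per patient.** 3 (rest) + 3 (10 W) + 3 (25 W) = 9, so at most 20 x 9 = 180 pairs. There are fewer if the age-predicted maximal heart rate stops the protocol (Appendix 3). Also in Appendix 3, the resting pacing-off period between +40 and +60 bpm lists no SWV measurement, so the SWV reference for those two steps is incomplete as written.

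**Shared reference.** With independent errors of equal variance v, a change has variance v + v/2 = 1.5v. Two neighbouring changes share one off-period and have covariance v/4. Their correlation from this source alone is 0.25/1.5 = 1/6.

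**Pooled test, clustering only.** Assumptions: no true link, no rate trend, equal intraclass correlation (ICC) in both measures. The documents give no ICC.

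Design effect = 1 + (9 - 1) x ICC(PCWP) x ICC(SWV). Effective pairs = 180/design effect. Approximate error = 2 x [1 - Φ(1.96/√design effect)].

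| ICC | Design effect | Effective pairs | Error, formula | Error, simulation |
|---|---|---|---|---|
| 0 | 1 | 180 | 5% | 5.1% |
| 0.3 | 1 + 8 x 0.09 = 1.72 | 105 | 14% | 14% |
| 0.5 | 1 + 8 x 0.25 = 3.00 | 60 | 26% | 24-26% |
| 0.7 | 1 + 8 x 0.49 = 4.92 | 37 | 38% | 37-39% |

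Simulations used 2,000 to 4,000 trials per scenario at N = 20. Spearman is within 2 points of Pearson. Mean r stays near 0: clustering shrinks the p-value but does not bias r. Pooling only the three steps of one workload gives 7.5%, 11.7% and 17.0% at ICC 0.3, 0.5 and 0.7.

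**Pooled test with a rate trend.** All trends are assumptions, with no link beyond the trend.

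| Trend over the three steps | Error of pooled Pearson | Mean r |
|---|---|---|
| PCWP falls and SWV rises by 0.5 SD per step | 50-55% (ICC 0.3-0.7) | about -0.15 |
| PCWP -1/-2/-3 mmHg, SWV +0.5/+1.0/+1.5 SD | 35.5% (ICC 0), 43.8% (0.5), 49.2% (0.7) | about -0.12 |
| Weaker, plateauing: PCWP -1/-2/-2 mmHg, SWV +0.25/+0.5/+0.75 SD | 7.8% (ICC 0), 26.4% (0.5) | about -0.03 |

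The shift in r follows from the step means. For the first row, three equally spaced steps give covariance -0.5 x 0.5 x 2/3 = -0.167 and variance 1 + 0.25 x 2/3 = 1.167 in each measure, so r = -0.167/1.167 = -0.14, in line with the simulation.

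**Alternatives, same no-link scenarios, N = 20.**
- One step per patient: error 4.4-6.1%. The 95% half-width at r = 0 is tanh(1.96/√(20 - 3)) = 0.44.
- One mean per patient: error 4.8-5.7%.
- Nine separate per-step tests: 1 - 0.95^9 = 37% chance of at least one false positive if the tests were independent.
- Within-patient correlation adjusted for step: error 4.7-6.0%.
- Repeated-measures correlation without step adjustment, under the 0.5 SD trend: about 77-100% rejection at ICC 0.3-0.7 (mean r -0.21 to -0.39). Removing patient means takes out between-patient noise but leaves the rate trend.

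**The case against.** A reader might infer that the plan treats nine values per patient as independent. The documents do not say so. Section 6.2 mentions no pooling, the endpoints are defined step by step, and section 2.4 describes pairwise comparisons, so a per-step correlation is at least as natural a reading. The promised SAP is where the unit would be set. This stands, and it limits the point to an unspecified unit with a conditional fault.

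A reader might also infer that no use of Pearson or Spearman could be sound here. That is too strong. One prespecified step, or one summary per patient, has independent pairs and holds about 5% error. A half-width of 0.44 is imprecision, not invalidity.

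The trend premise is uncertain too. The cited SWV finding comes from patients without HFpEF, and the background says the effect in HFpEF is unknown. The PCWP fall is hypothesised only up to an optimum. The 50% figure therefore needs a steady trend in both measures that the documents do not establish.

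Finally, the analysis is exploratory, and no primary or secondary endpoint depends on it. This stands and keeps the priority low. It does not remove the point: nothing in the documents fixes the unit, and the 5% level is applied to every test.

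**Conclusion.** The point holds as a gap with a conditional fault. Up to nine pairs per patient are collected, the unit of analysis is not stated, and the named method is valid only for one pair per patient.

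If steps are pooled over all conditions, the false-positive rate is about 14-39% for ICC 0.3-0.7 without a trend. It is about 50% with an opposite 0.5 SD-per-step trend, and about 8-26% with a weaker, plateauing one (ICC 0 to 0.5). The ICCs and trends are assumptions. Of the pooled scenarios, only zero ICC with no trend returned the nominal 5%. The rate trend, not the clustering, is what moves r away from zero.

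The documents do not support saying that the plan pools the steps, or that the primary conclusion is at risk. The repair is worth making but minor.

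**What to change.** In the SAP, replace the simple correlation with a linear mixed model of PCWP change on patient-mean-centred SWV change. Include a patient random effect, and pacing step, condition (rest, 10 W, 25 W) and their interaction as fixed effects. Centring matters: with uncentred SWV change, a random-intercept model in general blends within- and between-patient slopes. A repeated-measures correlation adjusted for step and condition is an acceptable equivalent. An unadjusted one is not, because it leaves the rate trend in.

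Report the within-patient slope with its 95% CI and keep it labelled exploratory. If a simple coefficient is still wanted, prespecify one step and condition, or one summary value per patient, and give its CI. State also how SWV change is formed at rest for the +40 and +60 bpm steps, given the off-period in Appendix 3 that lists no SWV measurement.

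The cost is one SAP line for the model and one for the SWV reference, using the data already planned and standard software. N = 20 and the primary analysis do not change.
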